8.1.4 Treatment/Evaluation Phase (Day 1)

Participants who start to experience prodromal symptoms before the visible appearance of any signs of HL must document the start time of symptoms in Science 37 Platform, complete a pre-dose (immediately before dosing) 0-10 NRS cold sore symptom evaluation (pain, burning sensation, itching and swelling) and a face image. Prior to the start of study intervention, all WOCBP participants MUST perform a urine pregnancy test, and verify that the results are negative (not pregnant), and record in the Science 37 Platform. After verification of a negative pregnancy test result, the participant may self-initiate study intervention.

Any participant who has a positive pregnancy test or is not sure of the results must contact the Science 37 study team immediately. Participants with a verified positive pregnancy test must not self-administer study intervention and will be withdrawn from the study.

Participants must always record pre-dose NRS and a face image irrespective of the start time of prodromal symptoms in the Science 37 Platform. After the completion of all pre-dose procedures, participants will be instructed to self-administer one (1) tablet. Should the buccal tablet adhere to the upper gum correctly, a second dose/tablet is NOT applied. A second tablet in the treatment kit is provided and labeled "BACKUP". The backup tablet should only be used if an issue occurs applying the first tablet (see Section 6.5).

After dosing, participants will complete the 0-10 NRS cold sore symptom evaluation, and face images at 09:00, 14:00 and 19:00 that day within Science 37 Platform. Depending on time of day study intervention is started, some Day 1 assessments and face images may not be collected if the time (minus the 60 minute window) occurs before the time of dosing. If dosing is started after 19:00, then post-dose NRS and face images will be collected starting the next day at 09:00. All post-dose time point assessments (NRS and face images) have an allowable window of ± 60 minutes.

Version 5.0

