8.2 Efficacy Assessments

8.2.1 Numerical Rating Scale (0-10)

Assessed at Screening (pre-dose), Day 1 through the participant's self-reported completion of study intervention (on Day 14). Participants will complete a NRS 0-10 symptoms scales for pain, tenderness, itching, tingling and discomfort for each time point. All post-dose time point assessments have an allowable window of ± 60 minutes.

My cold sore pain at this time is ...

| ту со іа | sore pai | n at this | iime is | • | | | | | | |
|---|------------------|------------------|------------|------------|------|---|---|---|---|---------------------------------|
| 0 | 1 | 2 | 3 | 4 | 5 | 6 | 7 | 8 | 9 | 10 |
| No pain | | | | | | | | | | Worst possible pain |
| The ten | derness o | f my colo | d sore at | this time | e is | | | | | |
| 0 | 1 | 2 | 3 | 4 | 5 | 6 | 7 | 8 | 9 | 10 |
| No tendern | iess | | | | | | | | 1 | Worst possible tenderness |
| The itch | ing of my | y cold so | re at this | time is | | | | | | |
| 0 | 1 | 2 | 3 | 4 | 5 | 6 | 7 | 8 | 9 | 10 |
| No itching | | | | | | | | | | Worst possible itching |
| The ting | ling of m | ıy cold se | ore at thi | is time is | | | | | | |
| 0 | 1 | 2 | 3 | 4 | 5 | 6 | 7 | 8 | 9 | 10 |
| No tingling | | | | | | | | | | Worst possible tingling |
| The discomfort of my cold sore at this time is | | | | | | | | | | |
| 0 | 1 | 2 | 3 | 4 | 5 | 6 | 7 | 8 | 9 | 10 |

Version 5.0 Page: 43 of 68

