Vesicular lesion: A lesion will be categorised as vesicular if a subject has face image interpretation Likert scale score of 3 or above.

Healing of primary lesions: A vesicular lesion will be considered as healed if the face image interpretation Likert score drops to either 0 or 1 after progressing to 3 and beyond. For those without a vesicular lesion, healing is defined as a face image interpretation Likert score of 0 or cessation of symptoms i.e., all NRS symptom scores as 0, whichever comes last.

Cessation of symptoms: Cessation of symptoms is defined as the absence of sensations of pain, tenderness tingling, itching or discomfort at the site of the cold sore as measured by NRS. In other words, having the NRS score of 0 for all symptoms such as pain, tingling, tenderness, itching and discomfort is cessation of symptoms.

Time to cessation of symptoms: It is the time (in hours) from the initiation of treatment dose of assigned study intervention to cessation of symptoms. For the subjects who do not demonstrate the cessation of symptoms, the data will be censored at 14 days (14*24 hours) regardless of any circumstances. If hour is missing for either treatment initiation or the endpoint but both dates are recorded, then Time to cessation of symptoms is number of days (end date – start date) multiplied by 24. If either date is missing, then Time to cessation of symptoms is missing.

 $\it Time\ to\ cess at ion\ of\ symptoms = (Date\ and\ time\ of\ cess at ion\ of\ symptoms - Date\ and\ time\ of\ first$

treatment administered)

Time to recurrence of HL lesions: It is the time (in days) from resolution of the cold sore treated in the Treatment phase until appearance of a cold sore during the follow-up period. The time to first recurrence is determined by assessment from the investigator and documented using NRS symptom scores and face images using the Science 37 Platform. For subjects who do not recur during the follow-up period, the data will be censored at the time of last follow-up.

Time to recurrence of HL lesions (Days) = (Date of first recurrence of HL lesions – Date of healing of primary lesions) + 1

CONFIDENTIAL Page 18 of 31

Private and Confidential Study No 21755 Date: DEC 18, 2023

Treatment Emergent Adverse Event: A TEAE is defined as any new AE that commences on or after the start of the first study drug administration or any pre-existed AE/ condition that worsened in severity following administration of study drug.

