5.3 Other Endpoints

Following are the **other endpoints** of the study:

- ➤ Duration of episode (DOE) will be measured in hours (using the Science 37 Platform), of a single treated HL lesion in subjects who initiation study intervention within 1 hour of onset of prodromal symptoms and subjects who initiated study intervention more than 1 hour after onset of prodromal symptoms.
- Time to cessation of symptoms, measured in hours from initial application of assigned study intervention. Cessation of symptoms is defined as the absence of sensations of pain, tenderness tingling, itching or discomfort at the site of the cold sore as measured by NRS.
- ➤ Quality of life score, as measured by the OHIP-14 questionnaire at 3-, 7- and 14-days post-dose.
- ➤ Global assessment of study intervention at Day 14.
- > The change from baseline to post-dose in NRS.
- The incidence of detachment or swallowing within 6 hours of dosing and the number (percentage) of subjects with the incidence.
- ➤ The percentage of subjects who replace the tablet among those with detachment or swallowing within 6 hours of dosing.

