7.7.3 Analysis of Other Efficacy Endpoints

The analysis of other endpoints will be performed on ITT population.

- **Duration of episode (DOE)** will be measured in hours (using the Science 37 Platform), of a single treated HL lesion in subjects who initiate study intervention within 1 hour of onset of prodromal symptoms and subjects who initiated study intervention more than 1 hour after onset of prodromal symptoms. DOE will be analyzed similarly to the analysis of primary efficacy endpoint using KM method. Individual subject data Listing for DOE will be presented.
- Fine to cessation of symptoms, measured in hours from the initiation of first dose of study drug. Cessation of symptoms is defined as the absence of sensations of pain, tingling, or burning at the site of the cold sore. Observation period to determine healing will last up to 14 days. Time to cessation of symptoms will be analyzed similarly to the analysis of primary efficacy endpoint using KM method. Individual subject data listing for Time to cessation of symptoms will be presented.
- ➤ Quality of life score, as measured by the OHIP-14 questionnaire at 3-, 7- and 14-days post-dose will be analysed using Cochran-Mantel-Haenszel (CMH) method with a modified ridit score. The number and percentage of subjects will be summarized for each question/item in OHIP-14 questionnaire by scheduled visits and treatment groups. The actual values of OHIP-14 weighted score for subscale category questions will be summarized by scheduled visits and treatment groups. The post-dose values will be compared between the Sitavig and placebo groups using two sample t-test assuming the normality of data and if the data is non-normal then Wilcoxon Rank-Sum test (also known as the Mann-Whitney U test) will be used. Please refer the Section 9.2 in this SAP for weight factors associated with subscale category questions. Individual subject data listing for OHIP-14 will be presented.
- ➤ Global assessment of treatment efficacy at Day 14 using a 5-point scale (0=none, 1=poor, 2=fair, 3=good, 4=excellent) will be analysed using CMH method with a modified ridit score. The number and percentage of subjects will be summarized for Global assessment of treatment efficacy. Individual subject data listing for Global evaluation will be presented.

CONFIDENTIAL Page 24 of 31

Private and Confidential Study No 21755 Date: DEC 18, 2023

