9 APPENDIX

9.1 Numerical Rating Scale (0-10)

Assessed at Screening (pre-dose), Day 1 through the subject's self-reported completion of study intervention (on Day 14). Subjects will complete a NRS 0-10 symptoms scales for pain, tenderness, itching, tingling and discomfort for each time point. All post-dose time point assessments have an allowable window of \pm 60 minutes.

My cold	sore pair	n at this i	ime is							
0	1	2	3	4	5	6	7	8	9	10
No pain										Worst
										Possible
										pain
The tend	erness of	my cold	sore at this	s time is						
0	1	2	3	4	5	6	7	8	9	10

CONFIDENTIAL Page 27 of 31

Private and Confidential Study No 21755 Date: DEC 18, 2023

No pain The itchi	i ng of my	cold sore	at this tin	ne is						Worst Possible pain
0	1	2	3	4	5	6	7	8	9	10
No pain The ting	ling of my	cold sore	e at this ti	me is						Worst Possible pain
0	1	2	3	4	5	6	7	8	9	10
No pain The disco	o mfort of	my cold s	ore at thi	s time is						Worst Possible pain
0	1	2	3	4	5	6	7	8	9	10
No pain			,					,	1	Worst Possible pain

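### Time to cessation of symptoms has two conflicting definitions, and the one in the analysis sections (SAP 7.7.3, protocol 9.4.4) cannot be fully derived from the symptom scale

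*SAP*

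**What the plan says.** The endpoint lists and the derivation section agree with one another. SAP 5.3 describes cessation as the "absence of sensations of pain, tenderness tingling, itching or discomfort at the site of the cold sore as measured by NRS". The protocol synopsis and protocol section 3 use the same five symptoms. SAP section 4 turns this into a rule: "having the NRS score of 0 for all symptoms such as pain, tingling, tenderness, itching and discomfort is cessation of symptoms".

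The sections that specify the analysis differ. SAP 7.7.3 states: "Cessation of symptoms is defined as the absence of sensations of pain, tingling, or burning at the site of the cold sore". Protocol 9.4.4 carries the same sentence.

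The instrument has five items. Protocol 8.2.1: "Participants will complete a NRS 0-10 symptoms scales for pain, tenderness, itching, tingling and discomfort for each time point". SAP 9.1 repeats this.

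Protocol 8.1.4 describes the score taken immediately before dosing with another list: "0-10 NRS cold sore symptom evaluation (pain, burning sensation, itching and swelling) and a face image".

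**The concern.** One endpoint should have one event rule. Here the section a programmer would open to produce the table names a symptom that the scale does not contain and leaves out three that it does. SAP 7.7.3 words its sentence as a definition and does not point back to section 4 for this endpoint, whereas SAP 7.7.1 does so for duration of episode. Neither document says which text governs.

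The rule fixes who has the event and when, so the Kaplan-Meier medians, the censoring, the log-rank test and the hazard ratio for this endpoint could all depend on it. If the choice is left open past database lock, it could be made after the data are seen.

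The list in protocol 8.1.4 raises a separate question: whether the pre-dose symptom scores cover the same items as the post-dose scores, which the NRS change-from-baseline endpoint needs.

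**Working it through.** The plan gives no figure for this point, so the check sets the lists side by side.

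| Symptom | SAP 7.7.3, protocol 9.4.4 | SAP 4, SAP 5.3, protocol synopsis and section 3 | Scale items: protocol 8.2.1, SAP 9.1 | Pre-dose list: protocol 8.1.4 |
|---|---|---|---|---|
| Pain | yes | yes | yes | yes |
| Tenderness | no | yes | yes | no |
| Itching | no | yes | yes | yes |
| Tingling | yes | yes | yes | no |
| Discomfort | no | yes | yes | no |
| Burning | yes | no | no | yes |
| Swelling | no | no | no | yes |

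**Can each rule be derived?** The five-symptom rule matches the scale item for item. The 7.7.3 rule names three symptoms, of which two (pain, tingling) are on the scale and one (burning) is not. Dropping burning leaves 5 − 2 = 3 measured symptoms unused: tenderness, itching and discomfort.

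**Which way do the times differ?** Let T2 be the first assessment with pain and tingling both at 0, and T5 the first with all five at 0. Any assessment that meets the second condition also meets the first, so T5 ≥ T2 for every participant. The same ordering holds if the zeros must be sustained.

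**What happens at the end of observation?** SAP section 4 censors at 14 × 24 = 336 h. A participant whose pain and tingling have gone, but who still reports tenderness, itching or discomfort at that point, has an event at T2 under the reduced 7.7.3 rule and is censored at 336 h under section 4.

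**How often would the rules disagree?** The documents give no data. For illustration only, assume that each symptom falls to 0 once and stays there, that the five are interchangeable, and that k of them clear together at the last step. The times differ only if neither pain nor tingling is among those k, which has probability C(3,k)/C(5,k):

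- k = 1: 3/5 = 60%
- k = 2: 3/10 = 30%
- k = 3: 1/10 = 10%
- k = 4 or 5: 0%

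The share therefore runs from 0% to 60% under interchangeability. Without that assumption it could lie anywhere from 0% to 100%.

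**Pre-dose items.** The 8.1.4 list shares two items with the scale (pain, itching). If it was followed literally, 5 − 2 = 3 items (tenderness, tingling, discomfort) would have no score immediately before dosing. SAP section 4 takes baseline as the latest available value before the first dose, and the schedule of activities collects the NRS at screening. Baseline for those three items would then be the screening score. Screening can fall up to 35 days before a run-in of up to six months, and the study scheme labels that visit's face image as symptom-free. Change from baseline would then use a prodromal baseline for pain and itching and a screening baseline for the other three.

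**The case against.** The strongest reply is that nobody would get this wrong. The five-symptom rule stands in the SAP's own definitions section, matches SAP 5.3, the synopsis, protocol section 3 and the scale, and is the only one of the two that can be computed as written. On that view the sentence in 7.7.3 is a leftover from protocol 9.4.4. Much of this stands: section 4 is very probably what is meant, and the endpoint is neither primary nor secondary. What does not stand is that the SAP settles it. It has no precedence clause, and a pain-and-tingling version can also be programmed from the data collected.

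A reader might infer four stronger things that the documents do not support:

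- **That primary duration of episode is exposed**, because cessation enters it for non-vesicular lesions. SAP section 4 writes the rule out for that purpose: "cessation of symptoms i.e., all NRS symptom scores as 0, whichever comes last". That derivation does not rely on 7.7.3.
- **That SAP 7.13 failed to declare a change.** SAP 7.7.3 carries over protocol 9.4.4 and SAP 5.3 carries over protocol section 3. The conflict was inherited, so there was no departure to declare.
- **That three symptoms would have no baseline.** The screening score would serve under the SAP rule. It may be old and symptom-free, but it is a value. Nor does the bracketed list in 8.1.4 show that the platform displayed a different form: 8.2.1 asks for the five items at every time point.
- **That the discrepancy can be sized against the 0.57-day effect quoted in protocol 2.2.** That figure is a difference between arms in healing of the primary lesion. A gap between two definitions within one participant is a different quantity, and either definition would apply to both arms.

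**Conclusion.** The inconsistency is real and should be corrected. Its extent is one endpoint with two definitions, present in both documents. One of the three symptoms named in 7.7.3 has no specified post-dose score, and three of the five measured symptoms are ignored if that rule is reduced to what can be computed. The direction of the effect on individual event times is certain (never later than under section 4). Its frequency, and any effect on the treatment comparison, cannot be determined from the documents.

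The pre-dose list in protocol 8.1.4 is a separate inconsistency. Its consequence is conditional: it matters for the NRS change endpoint only if the platform captured the 8.1.4 items instead of the five in 8.2.1. The case report form and platform screens are not among the documents, so this needs confirmation from the sponsor.

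**What to change.** 1. In SAP 7.7.3, replace the definition sentence with a cross-reference to the section 4 definition (NRS score of 0 for pain, tenderness, itching, tingling and discomfort), before database lock.
2. Make the same replacement in protocol 9.4.4 if the protocol can still be amended. If it cannot, the corrected SAP will differ from 9.4.4, and that difference should then be noted in SAP 7.13.
3. Reconcile the bracketed list in protocol 8.1.4 with the five items in 8.2.1, and confirm from the platform which items were captured before dosing. If tenderness, tingling or discomfort were not captured, state in the SAP that their baseline is the screening score and report the change endpoint with that limitation.

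The cost is a few words in each place and one check of the platform form. No new assessments are needed if the five scales were already shown before dosing; otherwise a small form change is needed for participants not yet dosed.

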8.1.5 Treatment/Evaluation Phase (Days 1 through 14)

8.1.5.1 Day 1-2 (Visit 2)

Within 36 hours after the start of study intervention, participants will present for Visit 2. Visit 2 can be performed on Day 1 or Day 2. The following procedures will be done for this visit:

- Review inclusion/exclusion criteria
- Review concomitant medications;
- Sitting BP and pulse after at least 5 minutes in a sitting position;
- Review Science 37 Platform data for completeness;
- Review study intervention kit (drug accountability);
- Review used/unused pregnancy test kits for signs of use;
- Adverse Event assessment.

Participants will record face images and complete 0-10 NRS HL symptom evaluation at 09:00, 14:00 and 19:00 that day in the Science 37 Platform. All post-dose time point assessments have an allowable window of ± 60 minutes.

8.1.5.2 Day 3

The following procedures will be done by the participant:

- Face images at 09:00, 14:00 and 19:00 that day;
- 0-10 NRS cold sore symptom evaluation at 09:00, 14:00 and 19:00 that day;
- QoL-OHIP at 09:00 that day;

All post-dose time point assessments have an allowable window of ± 60 minutes.

8.1.5.3 Days 4, 5 and 6

The following procedures will be done by the participant for each day:

- Face images at 09:00, 14:00 and 19:00 each day;
- 0-10 NRS cold sore symptom evaluation at 09:00, 14:00 and 19:00 each day.

All post-dose time point assessments have an allowable window of ± 60 minutes.

8.1.5.4 Day 7

The following procedures will be done by the participant:

- Face images at 09:00, 14:00 and 19:00 that day;
- 0-10 NRS cold sore symptom evaluation at 09:00, 14:00 and 19:00 that day;
- QoL-OHIP at 09:00 that day.

All post-dose time point assessments have an allowable window of ± 60 minutes.

Page: 40 of 68

Version 5.0 Page: 41 of 68

8.1.5.5 Days 8, 9, 10, 11, 12 and 13

The following procedures will be done by the participant:

- Face images at 09:00, 14:00 and 19:00 each day;
- 0-10 NRS cold sore symptom evaluation at 09:00, 14:00 and 19:00 each day;

All post-dose time point assessments have an allowable window of ± 60 minutes.

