2 STUDY DETAILS

2.1 Study Objectives

The primary objective of the study is:

➤ To compare Duration of Episode (DOE) of cold sores when treated with Sitavig or placebo in subjects experiencing a recurrence of Herpes Labialis (HL).

The secondary objectives of the study are:

- > To compare the incidence of aborted lesions between subjects receiving either Sitavig or placebo after experiencing prodromal symptoms of a recurrence of HL.
- To compare the incidence of recurrence of primary HL lesions between subjects receiving either Sitavig or placebo during a 12-month follow-up period.
- To compare the time to recurrence of primary HL lesions between subjects receiving either Sitavig or placebo during a 12-month follow-up period.
- > To assess safety and tolerability of the investigational products.

The other objectives of the study are:

- ➤ To compare the DOE in subjects who used Sitavig or placebo who initiated study intervention within 1 hour of prodromal symptoms and subjects who initiated study intervention after 1 hour of prodromal symptoms.
- > To compare the time to cessation of symptoms in patients experiencing a recurrence of HL in subjects who used Sitavig and placebo.
- > To compare the Quality of Life (QoL) in subjects who used Sitavig and placebo.

CONFIDENTIAL Page 8 of 31

Private and Confidential Study No 21755 Date: DEC 18, 2023

- ➤ To compare the 0-10 Numerical Rating Scale (NRS) HL symptoms by time point in subjects who used Sitavig and placebo.
- > To evaluate the Global assessment at Day 14.
- ➤ To evaluate the incidence of detachment or swallowing within 6 hours of dosing, and the incidence of replacing the tablet.

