4 DEFINITIONS AND DERIVATIONS

Run-in Failures: Run-in failures are participants who successfully completed screening and randomized to a blinded study intervention (treatment). Participants start a 6-month eligibility window during the Run-in Phase where they could potentially self-initiate treatment. Participants who are considered a Run-in failure occur because of the following:

- Randomized participants with no prodromal symptoms after 6 months
- Met an exclusion criterion (e.g., medication, pregnancy)
- Adverse event or change in medical history that requires study withdrawal
- Withdraw of informed consent by the participant
- Study intervention kit not available
- Lack of compliance as determined by the Investigator/designee

Baseline: Baseline value is defined as the last non missing assessment prior to first administration of the study drug. If the assessment occurs on the same day as the first study drug administration, then the time of assessment should be compared to the time of first dose administration to derive the baseline value.

Post-baseline: The Post-baseline values are defined as assessments taken after the first administration of study drug/treatment.

Change from Baseline = $(post\ baseline\ value - baseline\ value)$.

Duration of Episode (DOE): DOE is defined as the time from the initiation of treatment to the healing of primary lesions (loss of crust) for subjects who experience a vesicular lesion. For subjects whose primary lesions are not vesicular in nature, DOE is the time from study intervention initiation to the return to normal skin as determined by the independent blinded reader of the subject's face images using a 6-point Likert scale or the cessation of symptoms, whichever comes last. For the subjects who do not demonstrate the healing of primary lesions or cessation of symptoms, the data will be censored at 14 days (14*24 hours) regardless of any circumstances. If time (hour) is missing for either treatment initiation or the healing of primary lesion or both, however, both dates are recorded, then DOE is number of days (end date – start date) *24. If only healing ending date and/or time are missing, DOE will be imputed as 14*24 hours. If date of treatment initiation is missing, then DOE will be missing.

CONFIDENTIAL Page 17 of 31

Private and Confidential Study No 21755 Date: DEC 18, 2023

DOE (hours) = (Date and time of healing of primary lesions – Date and time of first treatment administered)

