- The change from baseline to post-dose in NRS. The actual and the change from baseline values of NRS score for each symptom/question will be summarized by scheduled visits and treatment groups. The change from baseline to post-dose values will be compared between the Sitavig and placebo groups using two sample t-test assuming the normality of data and if the data is non-normal then Wilcoxon Rank-Sum test (also known as the Mann-Whitney U test) will be used. Individual subject data Listing for NRS scores will be presented.
- The incidence of detachment or swallowing within 6 hours of dosing will be reported by treatment groups. The percentage of subjects with detachment or swallowing within 6 hours of dosing will be compared between the two treatment groups using the Chi square or Fisher's Exact test for homogeneity of proportions for categorical data. Individual subject data Listing for incidence of detachment or swallowing within 6 hours of dosing will be presented.
- ➤ The percentage of subjects who replace the tablet among those with detachment or swallowing within 6 hours of dosing will be analysed using the Chi square or Fisher's Exact test for homogeneity of proportions for categorical data. Individual subject data Listing of subjects who replace the tablet among those with detachment or swallowing within 6 hours of dosing will be presented.

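### Minor: the NRS change-from-baseline test omits the baseline covariate, and the baseline rule would let a pre-episode Screening score stand in for a missing Day 1 score; the cost is precision, not bias between arms

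*SAP*

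**What the plan says.** Change in NRS is one of the 'other' endpoints (SAP 5.3), analysed on the ITT population. The objective is by time point: "To compare the 0-10 Numerical Rating Scale (NRS) HL symptoms by time point in subjects who used Sitavig and placebo". For each symptom, SAP 7.7.3 tabulates actual and change values by visit and arm, then tests: "The change from baseline to post-dose values will be compared between the Sitavig and placebo groups using two sample t-test", or, "if the data is non-normal then Wilcoxon Rank-Sum test". No covariate is named in either case.

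The baseline comes from the general rule in SAP Section 4: "Baseline value is defined as the last non missing assessment prior to first administration of the study drug". It has no look-back limit and there is no NRS-specific version.

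Protocol 8.1.4 requires the Day 1 score: "Participants must always record pre-dose NRS and a face image irrespective of the start time of prodromal symptoms". At Visit 2 (Protocol 8.1.5.1) staff are to "Review Science 37 Platform data for completeness".

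Two inconsistencies bear on this.

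- **Screening NRS.** The study scheme, the Schedule of Activities, Protocol 8.2.1 and SAP 9.1 all place an NRS at Screening. The Screening procedure list in Protocol 8.1.1 has a baseline face image but no NRS.
- **Pre-dose items.** Protocol 8.1.4 describes the pre-dose score as a "0-10 NRS cold sore symptom evaluation (pain, burning sensation, itching and swelling) and a face image". Protocol 8.2.1 says "Participants will complete a NRS 0-10 symptoms scales for pain, tenderness, itching, tingling and discomfort for each time point", and SAP 9.1 has the same five items.

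**The concern.** A change score subtracts the whole baseline, which amounts to fixing the baseline coefficient at 1. When pre-dose and post-dose scores are only moderately correlated, that adds noise. Estimating the coefficient removes the excess, and the covariate is one the trial already requires.

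The problem is probably largest late in the 14 days. The Protocol introduction says cold sores last around 7 to 10 days, so many late scores are likely to be zero (an inference; no rate is given). When the post-dose score is zero, change is simply minus the baseline, and the test mostly compares pre-treatment variation.

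The baseline rule adds a second problem. If a Screening NRS exists and the Day 1 score is missing, the rule substitutes a score from before the treated episode. The study scheme labels the Visit 1 face image as symptom-free, so that score would often be near zero. Participants using the fallback would then be analysed on something close to the raw post-dose score, mixed with true changes from everyone else.

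The stakes are low: no primary or secondary endpoint uses NRS change.

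**Working it through.** The documents give no SD, correlation, missing rate or power for NRS, and the sample-size text is redacted. There is no plan figure to reproduce, and all numerical inputs below are assumptions.

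**1. Age of a Screening score.** Screening lasts up to 35 days (Protocol 8.1.1) and the run-in 6 months, taken as 183 days (Protocol 8.1.3): (35 + 183) / 30.4 = 7.2 months.

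**2. Change score against ANCOVA.** Let k = post-dose SD / pre-dose SD and ρ their correlation. In units of the pre-dose variance:

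- Var(change) ∝ 1 + k² − 2ρk
- Var(ANCOVA) ∝ k²(1 − ρ²)

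At k = 1 and ρ = 0.5 these are 1.00 and 0.75. The ANCOVA/change ratios are:

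| k | ρ = 0.3 | ρ = 0.5 | ρ = 0.7 |
|---|---|---|---|
| 0.5 | 0.24 | 0.25 | 0.23 |
| 1 | 0.65 | 0.75 | 0.85 |
| 1.5 | 0.87 | 0.96 | 1.00 |

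At k = 1 the change score needs 2/(1 + ρ) times as many participants: 1.54, 1.33 and 1.18.

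**3. The Wilcoxon option.** Simulation with 200 per arm and 3,000 runs per cell. Latent normal scores were rounded and clipped to 0–10: pre-dose mean 4, SD 2; post-dose SD 2 with mean 3 or 0; latent effect 0.5. Power at ρ = 0.3 / 0.5 / 0.7:

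| Post-dose zeros | Wilcoxon on change | Rank ANCOVA |
|---|---|---|
| about 11% | 47 / 62 / 82% | 70 / 77 / 90% |
| about 60% | 19 / 21 / 27% | 56 / 60 / 70% |

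Type I error was 0.044 to 0.055. A repeat of 2,000 runs agreed within simulation error.

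**4. The Screening fallback.** Let a share f have a Screening score of 0 as baseline, with pre-dose mean μ and common SD s:

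- Var(change) = (1 − f)·2s²(1 − ρ) + f·s² + f(1 − f)μ²
- Var(ANCOVA, missing covariate set to the mean) = s²[1 − ρ²(1 − f)]
- Shift in within-arm mean change = f·μ

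With μ = 3, s = 2, ρ = 0.5 and f = 0.10: change = 3.60 + 0.40 + 0.81 = 4.81; ANCOVA = 4 × 0.775 = 3.10.

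| f | Var(change) | Rise | Var(ANCOVA) | Change/ANCOVA | Mean shift |
|---|---|---|---|---|---|
| 0 | 4.00 | – | 3.00 | 1.33 | 0 |
| 0.05 | 4.43 | 11% | 3.05 | 1.45 | 0.15 |
| 0.10 | 4.81 | 20% | 3.10 | 1.55 | 0.30 |
| 0.20 | 5.44 | 36% | 3.20 | 1.70 | 0.60 |

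Mean imputation itself costs ANCOVA 1.7%, 3.3% and 6.7% in variance. At f = 0.10, over μ 2–4, s 2–2.5 and ρ 0.3–0.7, the change/ANCOVA ratio runs from 1.25 to 1.87.

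**5. Bias.** Baseline precedes dosing, so under blinding a missing Day 1 score cannot depend on the treatment received. In 20,000 simulated null trials (200 per arm) the mean arm difference stayed within 0.003 of zero. A separate simulation (150 per arm) with sicker participants more often missing a true effect gave −0.600 with the fallback and −0.603 with complete baselines.

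**The case against.** The strongest reply is that this is a preference. A two-sample test on a prespecified 'other' endpoint is valid, and the visible text claims no power for it. That is right, and it is why the point is graded minor.

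The fallback is also conditional. It needs a Screening NRS, on which the documents disagree, and a missing mandatory entry. Both conditions stand. The Visit 2 review offers limited protection, however: it may take place up to 36 hours after dosing and cannot recover a score due immediately before it.

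Nor does the fallback always add noise. With s = 2.5, ρ = 0.3, f = 0.10 and a pre-dose mean of 1, the same formula gives 7.875 + 0.625 + 0.09 = 8.59 against 8.75 with none missing, a fall of 1.8%; with a mean of 0.5 the fall is 2.6%. Early dosing makes low means possible. The exception is real but small.

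The Wilcoxon power gap is largely the penalty for subtracting baseline in full. With about 60% zeros, an unadjusted Wilcoxon on post-dose scores reaches 54 / 54 / 52%, so at ρ = 0.3 the covariate adds little beyond that. This is a fair account of where the gain comes from, but an estimated baseline coefficient removes that penalty and also uses what correlation there is.

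Finally, if the four-item list in Protocol 8.1.4 was followed literally, tenderness, tingling and discomfort have no Day 1 score, and no covariate exists for them. The gain therefore depends on checking what was recorded.

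**Conclusion.** The point holds as a minor one. The facts of the text are certain: no covariate in the NRS test, no age limit on baseline, and two unreconciled descriptions of what is scored and when. The planned comparison is valid and, on average over randomisations, unbiased between arms. The tabulated within-arm changes are different: any fallback to a symptom-free Screening score would shift them in both arms alike.

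The size is uncertain because every input is assumed. For the t-test the ANCOVA/change variance ratio runs from about 0.23 to 1.00 over the range examined, so the gain may be large at late, zero-heavy time points and nil if post-dose scores are much more variable than pre-dose scores. The fallback matters only if Day 1 scores are missing in some number, and the documents give no rate. The mismatch in item lists does not show that any baseline was lost.

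**What to change.** 1. **SAP 7.7.3.** For each symptom at each scheduled time point, compare post-dose NRS (equivalently, change) by ANCOVA or a repeated-measures model with the Day 1 pre-dose score as covariate. This keeps the by-time-point objective and the descriptive tables. Prespecify a rank-based ANCOVA for zero-heavy scores in place of Wilcoxon on change.
2. **SAP Section 4.** Define NRS baseline as the Day 1 pre-dose score, with no Screening fallback. Handle a missing covariate by a prespecified method that ignores arm, such as mean imputation, and leave that participant out of the descriptive change summary.
3. **Consistency.** Reconcile the pre-dose items in Protocol 8.1.4 with the five in Protocol 8.2.1 and SAP 9.1, and state whether NRS is scored at Screening. Check which items the platform recorded before dosing. For any item with no Day 1 score, say so and compare post-dose scores without that covariate.

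The cost is SAP wording, standard model code and one check of the recorded items. No new data are needed.
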